7.8.1.5 Exposure adjusted analysis of adverse events

For a specific AE, the total AE time at risk [years] is defined as the sum of time at risk [days] across all contributing patients / 365.25, with for each patient the time at risk [days] defined as follows:

- Date of first start of AE – date of first study medication administration +1 day for patients with the specific AE
- End of time at risk – date of first study medication administration + 1 day for patients without the specific AE

For the AE analyses over 52 weeks, the end of time at risk is the end of the REP for patients who discontinue prior to week 52 or day 373 for patients who do not discontinue prior to

week 52. For the AE analyses over the whole trial, the end of time at risk is the minimum of either “+28 days after termination of trial mediation” or the date of the corresponding database lock.

The AE incidence rate [1/100 Patient years (pt-yrs)] = 100 * number of patients with specific AE / total specific AE time at risk [years]. The 95% confidence intervals for incidence rates are derived using the method described by Rothman and Greenland (2008) ([19](#)).

The incidence rate ratio for a given AE is defined as the incidence rate of that event in patients in the Nintedanib 150mg bid treatment group divided by the incidence rate of that event in the Placebo group. The estimates and 95% confidence intervals for incidence rate ratios are based on a Cochran-Mantel-Haenszel test.

The incidence rate difference for a given AE is defined as the incidence rate of that event in patients in the Nintedanib 150mg bid treatment group minus the incidence rate of that event in the Placebo group. The estimates and 95% confidence intervals for incidence rate differences are derived based on the method described in Greenland and Robins (1985) ([20](#)).

For this trial, separate frequency tables based on SOC and PT, but also on safety topic level, will be created for the week 52 analyses as well as for the analyses over the whole trial, for the overall population, showing the incidence rate, incidence rate ratio and incidence rate difference (each with 95% confidence interval) per the aforementioned specifications, and added to Section 16.1.13.1.

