5. ENDPOINTS

In this section, more details are given regarding endpoints. Note that for all endpoints and analyses, [Section 6.7](#) should be consulted for baseline value definition. For analyses that are specified over 52 weeks (Part A), unless otherwise specified, all data (including baseline) up to week 52 (inclusive – as defined in [Section 6.1](#)) will be taken into account, including follow-up visits before week 52 for patients who discontinue the trial medication prematurely. Analyses over the whole trial (Part A and Part B) reported at the time of the benefit-risk analysis will be based on all data collected until the data cut-off for DBL1. Analyses over the whole trial (Part A and Part B) reported after the final database lock (DBL2) will be based on all data collected within the trial.

Handling of missing data points is described in [Section 6.6](#).

For endpoints where the “date of last contact” is utilised, the following will apply:

- The last contact date when the patient was known to be alive is defined as the latest date recorded in the electronic Case Report Form (eCRF) from the dates listed below (in case a date is planned to be imputed for the analysis, the imputed date will also be used for the definition of “date of last contact”):
 - Date of last visit (e.g. for spirometry), data of last reported Adverse Event (AE) (excluding censored dates), date of last reported concomitant treatment, date of last laboratory sample, date of last drug intake, date of last reported dose change / interruption, last contact date (as documented on the termination of trial eCRF page if the reason for not completing the planned observation period is NOT “Death”), vital status date (from the vital status eCRF page if the patient is known to be alive) and the latest of vital status date / last successful contact date (from the vital status eCRF page if the patient was lost to follow-up).

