3	Patient did not have a documented first liver enzyme elevation within the first 52 weeks or before the treatment was prematurely ^[1] discontinued and the end of the REP has been reached.	Censored	If day of last drug intake < 372 days after first drug intake: Date of last drug intake +28 days or date of death (if earlier) ^[2] If day of last drug intake \geq 373: Date of first drug intake + 372 days

[1] Prematurely: Discontinuation of the treatment before completion of Visit 9.

[2] Patients that die between date of permanent drug discontinuation and the end of the residual effect period will be censored at their date of death

Table 5.4.4: 2 Censoring Rules for Time to first liver enzyme elevation over the whole trial

Rule #	Situation	Outcome (event or censored)	Date of event or censoring
1	Patient had a documented first liver enzyme elevation before the treatment was permanently discontinued and the date of the event is known	Event	Date of event
2	Patient had a documented first liver enzyme elevation before the treatment was permanently discontinued and the date of the event is unknown	Event	Imputed date of event
3	Patient did not have a documented first liver enzyme elevation before the treatment was permanently discontinued	Censored	Earliest date of database lock, date of permanent drug discontinuation + 28 days or date of death ^{[1][2][3]}

^[1] Date of permanent drug discontinuation may not have been reached when the primary analysis takes place. In this case, the date of database lock will be used.

^[2] Patients who switch to the extension study will only be evaluated until date of last drug intake in this study. The residual effect period will not apply, as patients will receive continuous treatment

^[3] Patients that die between date of permanent drug discontinuation and the end of the residual effect period will be censored at their date of death.

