6.1.2 Over the whole trial

For efficacy and safety analyses over the whole trial period (Part A and Part B), data from first drug intake up to the last visit in the trial will be considered. Please see Table 6.1.2: 1 for details about analysis periods over the whole trial (Part A + Part B) according to the type of endpoint. For the main analysis only data collected over the whole trial available at the time of data cut-off for DBL1 will be considered, whereas all data collected within the trial will be considered and reported for the final analysis.

Table 6.1.2: 1 Summary of analysis periods over the whole trial (Part A and Part B) according to the type of endpoint or analysis

Type of analysis	Analyses / Endpoints	Studied period	
		Start date ^[2]	End date ^{[1][4]}
Efficacy analyses	Analyses on all endpoints listed in Sections 5.1.3.2 of the CTP	Date of first drug intake	Date of last measurement up to the last follow-up visit (included) or last contact date (as defined in Section 5)
Descriptive analyses over the trial period	Absolute change from baseline in: 
• FVC (ml)• FVC (% of predicted)• DLCO (% of predicted)• Vital signs Relative change from baseline in : 
• FVC (% of predicted)	Date of first drug intake	Date of last measurement up to last follow-up visit (included)
Efficacy survival analysis	Time to all-cause mortality (over the trial period)	Date of first drug intake	Last contact date (as defined in Section 5)
Extent of exposure analysis overall	See Section 5.4.3	Date of first drug intake	Date of last drug intake
Safety survival analysis ^[3]	Time to 
• first liver enzyme elevation (for all definitions mentioned in Section 5.4.4)• first onset of adverse event with additional information collection (diarrhoea, bleeding, ILD)	Date of first drug intake	Date of last drug intake + 28 days
	Time to 
• first dose reduction• first treatment interruption• premature treatment discontinuation	Date of first drug intake	Date of last drug intake
On-treatment safety analysis overall ^[3]	
• Adverse events• Laboratory data• Vital signs	Date of first drug intake	Date of last drug intake + 28 days

[1] End date is included.

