[2] Date of randomisation and date of first drug intake should be identical. If there are discordances between these dates on patient level, date of first drug intake will be used.

[3] Patients who switch to the extension study will only be evaluated until date of last drug intake in this study. The residual effect period will not apply, as patients will receive continuous treatment.

[4] For the main analysis only data collected over the whole trial available at the time of data cut off for DBL1 will be considered, whereas all data collected within the trial will be considered and reported for the final analysis.

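### The whole-trial AE time-at-risk rule (SAP 7.8.1.5) runs past the SAP's own event windows, so read literally it understates whole-trial incidence rates

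*SAP*

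**What the plan says.** SAP 7.8.1.5 divides the number of patients with a given AE by the summed time at risk. A patient with the AE contributes time up to first onset. A patient without it contributes time up to an end date.

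- **52-week analysis:** "the end of time at risk is the end of the REP for patients who discontinue prior to" week 52, and day 373 for everyone else.
- **Whole-trial analysis:** the earlier of 28 days after termination of trial medication "or the date of the corresponding database lock".

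Neither rule mentions death. The whole-trial rule mentions neither the data cut-off nor roll-over into the extension trial.

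Elsewhere the SAP is narrower:

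- **Cut-off.** Section 6.1.2 says that for the main analysis "only data collected over the whole trial available at the time of data cut-off for DBL1 will be considered". Section 5 says that whole-trial analyses reported at the benefit-risk assessment "will be based on all data collected until the data cut-off for DBL1".
- **Roll-over.** Footnote 3 of Table 6.1.2: 1, attached to the on-treatment AE row, says "Patients who switch to the extension study will only be evaluated until date of last drug intake in this study" and adds "The residual effect period will not apply, as patients will receive continuous treatment". Section 6.1 also cuts the residual effect period short at the first extension-trial dose.
- **Death.** Table 5.4.4: 2 censors time to first liver enzyme elevation at "Earliest date of database lock, date of permanent drug discontinuation + 28 days or date of death". Table 5.4.4: 1 also stops at death. Section 7.8.1.4 applies both tables to the diarrhoea, bleeding and ILD plots. Table 5.4.4: 2 respects death and roll-over but still uses the lock rather than the cut-off.

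**The concern.** A rate needs a numerator and a denominator taken over the same window. Under 7.8.1.5 the denominator can include three kinds of days in which no event can be counted: days between cut-off and lock for ongoing patients, up to 28 days after roll-over, and up to 28 days after death. Roll-over patients need no follow-up visit (Protocol 6.2.3), and investigators need not actively monitor AEs after a patient's end of trial (Protocol 5.3.7), so those 28 days are not properly observed here.

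The whole-trial AE summaries (SAP 7.8.1.2), the whole-trial subgroup outputs (Table 7.4.3: 1, footnote 2) and the rate, ratio and difference tables of 7.8.1.5 all use these rates. In a placebo-controlled safety comparison, understated rates err in the non-conservative direction. Two programmers, one following 7.8.1.5 and one following 6.1.2, would also produce different denominators.

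**Working it through.** **1. Where the rules conflict**

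| Limit | SAP 7.8.1.5 | Elsewhere in the SAP | Analysis affected |
|---|---|---|---|
| Data cut-off | not named; lock used | 5 and 6.1.2: data to cut-off | DBL1 only |
| Roll-over | not named; +28 days | 6.1 and 6.1.2: no or shortened residual effect period | DBL2 only |
| Death | not named | Tables 5.4.4: 1 and 2: stop at death | all, including 52 weeks |

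For a patient who stops drug, survives and does not roll over, last dose + 28 days matches the event window in 7.8.1, so there is no conflict unless the cut-off falls inside those 28 days.

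**2. Inputs**

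The plan states no incidence rate, person-time or cut-off-to-lock interval, so there is no figure to reproduce. For illustration, the IPF percentages in Protocol 1.2 are used (nintedanib / placebo): deaths over 52 weeks 5.5% / 7.8%, AE leading to discontinuation 19% / 13%, AST and/or ALT ≥3x ULN 5.0% / 0.7%, diarrhoea 62.4% / 18.4%.

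Assumptions not in the documents: constant hazards, uniform accrual over 12 or 18 months, a gap of 0 to 12 weeks, and, for DBL2, 12-month accrual, 120 further days of follow-up and roll-over of every patient still on drug. Death on drug is treated as the last dose.

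**3. Formula**

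Rate = 100 × patients with AE / years at risk. With the numerator fixed, the change in rate is (correct time / written time) − 1.

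**4. Hand check, placebo arm, rare AE**

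Yearly hazards, −ln(1 − p): death 0.0812, discontinuation 0.1393, sum 0.2205.

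*52 weeks.* Share off drug before day 372: 1 − exp(−0.2205 × 372/365) = 0.201. Of these, 0.0812/0.2205 = 36.8% leave by death, that is 0.074 of all patients. Days wrongly added: 0.074 × 28 = 2.1 per patient. Correct mean time: 0.2012/0.2205 years = 333 days, plus (0.201 − 0.074) × 28 = 3.6, about 337 days. 2.1/337 = 0.6%.

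*DBL1, 12-month accrual, 4-week gap.* Follow-up to cut-off is uniform from 372 to 737 days. The share still on drug is the average of exp(−0.2205t) over that range, 0.717. Of the 0.283 off drug, 36.8% (0.104) left by death and 0.179 by discontinuation. Correct mean time: 0.2832/0.2205 = 1.284 years, plus 0.179 × 28 days (0.014 years), gives 1.298 years. Days added: 0.717 × 28 + 0.104 × 28 = 23.0 days = 0.063 years. 0.063/1.298 = 4.9%, a fall in the rate of about 4.6%. At 12 weeks: 0.717 × 84 + 2.9 = 63.1 days = 0.173 years, or 13.3% more time and a rate about 11.8% lower.

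**5. Simulation, 400,000 patients per arm**

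Change in rate, rule as written against the truncated rule. DBL1 ranges cover the two accrual periods.

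| Analysis | ALT/AST, nintedanib | ALT/AST, placebo | Diarrhoea, nintedanib | Diarrhoea, placebo |
|---|---|---|---|---|
| 52 weeks | −0.43% | −0.62% | −0.43% | −0.61% |
| DBL1, no gap | −0.42% | −0.60 to −0.61% | −0.42 to −0.43% | −0.61% |
| DBL1, 2 weeks | −2.06 to −2.38% | −2.36 to −2.70% | −1.13 to −1.35% | −2.10 to −2.42% |
| DBL1, 4 weeks | −3.62 to −4.24% | −4.05 to −4.69% | −1.81 to −2.25% | −3.53 to −4.15% |
| DBL1, 8 weeks | −6.55 to −7.72% | −7.23 to −8.40% | −3.14 to −3.99% | −6.23 to −7.38% |
| DBL1, 12 weeks | −9.27 to −10.89% | −10.14 to −11.78% | −4.42 to −5.61% | −8.76 to −10.36% |
| DBL2, all completers roll over | −3.41% | −3.85% | −1.57% | −3.31% |

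The hand check agrees. The common AE is less affected because patients who have it stop contributing at onset.

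**6. Between-arm measures** (12-month accrual, 4-week gap)

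- Diarrhoea: correct 97.78 against 20.30, ratio 4.82, difference 77.48. As written 95.58 against 19.46, ratio 4.91, difference 76.12. The ratio rises and the difference shrinks.
- An AE with a true rate of 5.00 in both arms, using the ALT/AST changes: 5.00 × 0.9576 − 5.00 × 0.9531 = +0.02. A null difference becomes slightly positive.

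**The case against.** The strongest reply is that 7.8.1.5 is shorthand. Section 6.1.2 has a row for on-treatment AEs, its footnotes impose the cut-off and the roll-over rule, and 6.1 ends the residual effect period at the first extension dose. That stands in part. A reader might infer that the plan has no such limits at all, and the documents do not support that: for cut-off and roll-over this is an internal conflict. It does not remove the problem, because 7.8.1.5 is the specific rule for the denominator and gives a different end date. Death has no general AE rule anywhere.

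Second, Protocol 3.1 and SAP 3 place the lock at the time the last patient reaches week 52, and the SAP also uses the lock as a censoring date in Tables 5.4.3.2: 1 to 3. The terms may be used loosely and the gap may be short. That stands: with no gap, the cut-off component vanishes.

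Third, consequences are limited. Whole-trial safety data are descriptive, no safety hypothesis is tested (Protocol 7.3 and 7.3.4), and the ratio and difference tables go to an appendix of the report. That also stands. It bears on priority, not on whether the rule is right.

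**Conclusion.** The rule should be corrected. As written, it counts time in which no event can be counted, and whole-trial rates per 100 patient-years come out too low. The size depends mainly on the undocumented cut-off-to-lock gap: for an uncommon AE at DBL1, about 0.5% with no gap, 4-5% at 4 weeks and 9-12% at 12 weeks. At DBL2 it is about 2-4% if all completers roll over. These figures rest on IPF event rates and the accrual assumptions above.

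Four stronger readings are not supported:

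- *The 52-week rates, which carry the primary benefit-risk assessment, are materially wrong.* Lock, cut-off and roll-over play no part there. Death alone moves them by about 0.4-0.6%. That assumes death on drug counts as discontinuation. If it did not, time would run on to day 373.
- *Rate differences are always biased low.* They shrink toward zero or shift with the balance of ongoing patients between arms, and ratios can rise.
- *Person-time is inflated by up to about 21%.* That needs 90% of patients ongoing, a 12-week gap and mean exposure of 1.0 year (0.9 × 84/365 = 0.21). At DBL1 every patient has at least 52 weeks of potential follow-up and early enrollers more, so this is a corner case. It also ignores that patients with the AE stop contributing at onset.
- *The components add up.* Cut-off acts only at DBL1 and roll-over only at DBL2.

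**What to change.** In SAP 7.8.1.5, define the end of whole-trial time at risk as the earliest of last dose + 28 days, death, the data cut-off (DBL1 analysis) and, for patients who roll over, last dose in this trial. State that events are counted in the same window. Add death to the 52-week rule.

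In Table 5.4.4: 2, replace the database lock by the data cut-off for the DBL1 analysis. This also corrects the diarrhoea, bleeding and ILD plots. The lock wording in Tables 5.4.3.2: 1 to 3 can be aligned at the same time.

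The cost is SAP wording and one derivation. All the dates needed are already collected or set by the sponsor.

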7.8.2 Laboratory data

The analyses of laboratory data will be descriptive in nature and based on SI units according to BI standards ([11](#)). Please refer to Section 7.3.4 of the CTP for further details. All analyses will be performed on the co-primary populations as well as on the complementary patient population. The main focus of the analysis of laboratory parameters will be on the first 52 weeks; however, all analyses of laboratory data will be repeated with data collected over the whole trial for all analyses populations.

Descriptive statistics for laboratory tests based on US conventional units will be provided in addition for the co-primary populations as well as on the complementary patient population, covering both analysis periods “over 52 weeks” and “over the whole trial”. All of these outputs will be part of the CTR appendix.

7.8.2.1 Over 52 weeks

A thorough description of liver enzymes and bilirubin elevations over 52 weeks will be given, as defined in [Section 5.4.4](#), including a display of maximum individual elevation. A summary table of liver enzymes and bilirubin elevations over 52 weeks will also be provided (please refer to [Table 6.7: 4](#) for time windowing definition). The time to onset of first liver enzyme and bilirubin elevation [days] will be summarized by categories ($\geq 1 - \leq 30$; $\geq 31 - \leq 60$; $\geq 61 - \leq 90$; ≥ 91). For each patient having experienced a liver enzyme and bilirubin elevation, a graphical representation of AST, ALT and bilirubin over time will be provided. In addition, a Kaplan-Meier plot of time to first liver enzyme elevation (if at least 5% of patients show liver enzyme elevations) will be created and evaluated

7.8.2.2 Over the whole trial

The analysis of liver enzyme elevations over the whole trial will be performed as depicted in [Section 7.8.2.1](#) above.

7.8.3 Vital signs

7.8.3.1 Over 52 weeks

Summary statistics will be presented for observed values and change from baseline by treatment and visit. The frequency of patients with marked changes in vital signs over 52 weeks will also be summarised by treatment according to the endpoints defined in [Section 5.4.5](#) of this document. Please note that these evaluations are prepared for the co-primary populations, as well as in the complementary population.

7.8.3.2 Over the whole trial

The analysis of vital signs over the whole trial will be performed as depicted in [Section 7.8.3.1](#) above.

7.8.4 ECG

Not applicable.

7.8.5 Others

Not applicable.

9. ADDITIONAL SECTIONS

9.1 K-BILD SCORING INSTRUCTIONS

9.1.1 Overview

The K-BILD is comprised of 15 items in three distinct health status domains, including breathlessness and activities (items 1, 4, 11, and 13), chest symptoms (items 2, 7, and 9), and psychological (items 3, 5, 6, 8, 10, 12, and 14) domains. A final item is used to assess the impact of the respondent's lung condition on their financial state. Rasch analysis confirmed the 15 items could be combined into a total score (12). The domain and total scores each range from 0–100, and higher scores indicate a better health status.

Response options for all 15 items are on a 7-point Likert scale, ranging from 1 to 7. For each of the items, the response options vary, including: item 1 (1 = "Every time," 7 = "Never"); items 2–4, and 6–14 (1 = "All of the time," 7 = "None of the time"); item 5 (1 = "None of the time," 7 = "All of the time"); and item 15 ("A significant amount," 7 = "Not at all").

9.1.2 Scoring Algorithm

To score the K-BILD, the Likert response scale weightings for individual items are combined, to ensure they detect progressive change in health status. Table 9.1.2: 1 shows the recoded scale weightings associated with each raw, item-level score value. Raw domain and total scores are then calculated by summing the recoded scale values provided in that table.

Table 9.1.2: 1 K-BILD Response Option Weightings

Item	Response						
	1	2	3	4	5	6	7
1	0	1	2	3	4	5	6
2	0	0	1	1	2	2	3
3	0	1	2	3	4	5	6
4	0	0	1	1	2	2	3
5	0	0	1	1	1	2	2
6	0	1	2	3	4	5	6
7	0	0	1	1	2	2	3
8	0	0	1	1	2	2	3
9	0	0	1	1	1	2	2
10	0	1	2	3	4	5	6
11	0	1	2	3	4	5	6
12	0	1	2	3	4	5	6
13	0	1	2	3	4	5	6
14	0	1	2	3	4	4	5
15	0	0	1	1	1	2	2

Finally, the raw domain and total scores are transformed to a range of 0–100 by using logit values and a simple look-up table to yield interval-level scores, where higher scores indicate better health status. Thus, for each raw summed domain and total score, look up the corresponding transformed domain and total score from Table 9.1.2: 2 below.

Table 9.1.2: 2 K-BILD Score Transformations

Breathlessness and Activities		Chest Symptoms		Psychological		Total	
Raw Score	Transformed Score	Raw Score	Transformed Score	Raw Score	Transformed Score	Raw Score	Transformed Score
0	0	0	0	0	0	0	0
1	10.4	1	17.3	1	10.6	1	9.2
2	17.7	2	32.1	2	17.5	2	15.3
3	22.9	3	44	3	21.9	3	19.4
4	27	4	54.3	4	25.3	4	22.6
5	30.3	5	63.7	5	28	5	25.1
6	33.1	6	73.4	6	30.2	6	27.2
7	35.6	7	85.2	7	32.2	7	29
8	37.8	8	100	8	33.9	8	30.5
9	39.9			9	35.5	9	32
10	41.9			10	37	10	33.3
11	43.9			11	38.5	11	34.4
12	45.9			12	39.8	12	35.5
13	48			13	41.2	13	36.5
14	50.2			14	42.5	14	37.5
15	52.5			15	43.8	15	38.4
16	55.2			16	45.1	16	39.3
17	58.5			17	46.4	17	40.1
18	62.7			18	47.7	18	40.9
19	68.8			19	49.1	19	41.7
20	79.9			20	50.5	20	42.4
21	100			21	52	21	43.2
				22	53.5	22	43.9
				23	55.2	23	44.6
				24	56.9	24	45.2
				25	58.8	25	45.9
				26	60.8	26	46.5
				27	63	27	47.2
				28	65.5	28	47.8
				29	68.3	29	48.5

Table 9.1.2: 2 K-BILD Score Transformations (continued)

